By applying this electrophysiologic principle of differential tissue capture to help identify the location of the compact AV node, which is in close proximity to the His bundle. Ventricular pacing was performed initially at high output to capture both the basal right ventricular myocardium and the His bundle and the output was gradually lowered to lose His bundle capture. The QRS duration is relatively narrow with high output pacing and increases when the pacing output is lowered, representing ventricular myocardial capture alone. Finally, loss of ventricular capture is seen with further reduction of pacing output. This maneuver has been shown to aid in determining the proximity of the ablation catheter to compact AV node as was validated by successful ablation at this site. Parahisian pacing in conjunction with av nodal ablation has recently been described in the literature [4-5].

A novel catheter with three mini electrodes within the ablation tip (IntellaTip MiFi, Boston Scientific, Boston, MA) may enhance the available data for such a signal dependent technique. In this catheter, bipolar signals can be recorded between the three 0.8-mm-wide electrodes that

are arranged radially 1.3 mm from the end of the catheter alongside the standard distal and proximal bipolar recordings. Animal studies have already demonstrated that the mini electrodes in this novel catheter are more accurate in identifying conducting gaps in linear ablations than conventional electrode recordings [6].

Study Aims:

The aim of our study is to investigate the comparative efficacy of high fidelity multi electrode ablation catheters vs the standard bipolar configuration in success of AV nodal ablation. Both catheters are FDA approved and are being used as indicated on its label. For the purpose of this study, the standard bipolar catheter will be 8mm non-irrigated, and from the following list: Boston Scientific Blazer, Biosense Thermocool Non-Nav, and the St. Jude Sapphire. All of these catheters are currently used in ablation cases at the study site. This study will provide insights on the use of new technology where application may increase efficacy, promote patient and physician safety and decrease costs.

Primary and secondary objectives

Primary endpoints

1. Acute success of ablation identified by a junctional rhythm or complete heart block
2. Time from application of radiofrequency energy to acute success

Secondary endpoints include

1. Procedure time
2. Radiation time

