3. Frequency of ablation application
4. Duration of ablation application

Research Plan

Inclusion Criterion

1. Patients with a diagnosis of **persistent or permanent atrial fibrillation** documented on electrocardiography
2. Patients must meet ACC/HRS guidelines for atrioventricular nodal ablation procedure
3. Patients have already been scheduled for their standard of care ablation
4. Patients must be available for at least 1 month post procedure
5. Patients must be greater than or equal to 18 years old.

Exclusion Criterion

1. Patients who do not meet ACC/HRS indications for av nodal ablation
2. Women who are pregnant

Research Design

The study will be performed at the University of Florida Health Science Center at UF Health, Jacksonville-Division of Cardiology. Patients will be recruited in the Cardiology Clinics of our institution and will be screened by Cardiology Research Staff, who will verify all
NCT03114124 1/25/2021

candidates meet inclusion and exclusion criteria.

Patients found eligible, n=30 for this study will already have a diagnosis of atrial fibrillation and be indicated for an ablation per standard of care. After providing written informed consent, subjects will be randomized by random computer programming to receive an ablation with MIFI technology or standard ablation catheter for their procedure. Data will be collected prospectively (perioperatively and at follow up visit).

During the ablation each patient will have a 3D electroanatomical map of the his bundle region created in addition to pacing along the region of interest. The target will be where the HIS electrogram amplitude is greatest and where the QRS complex from pacing is narrowest. Data will be collected until the primary endpoint of success is achieved.

Subjects will return to UF Shands -Jacksonville on day 30(+/- 14 days) to assess underlying conduction. If conduction has returned they will be offered an additional av nodal ablation per standard of care. If they undergo additional ablation this data will be included

Statistics

Sample Size Justification

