This is a pilot study in which the primary aim is to estimate the time until successful end point in each of the two study arms. Thirty patients will be randomized (15 in each study arm). Variable block sizes will be used to improve the blinding of the clinical team. This information will then be used to design a fully-powered randomized study to compare these two arms. Patients will be randomly assigned to study arms. The project biostatistician and team will generate a set of envelopes which contain the random assignments for each patient. Once a patient has consented to participate, the next envelope will be opened for that patient and the catheter assignment will be revealed. This will maintain the blinding of NCT03114124 1/25/2021

the clinical team.

Statistical Analyses

The baseline demographic and clinical characteristics of the patients included in this study will be summarized by study arms. Frequencies and percentages will be summarized for categorical variables and means, standard deviations, medians, minima, and maxima will be summarized for numeric variables. For ordinal variables, the medians, minima, and maxima will be summarized. Based on the descriptive summaries and graphical summaries (e.g. box-and-whiskers plots), if there are individual baseline characteristics that differ between the study arms, these characteristics will be included a regression analysis to reduce the estimated variance of the difference between the study arms.

The primary analysis is the estimation of Kaplan-Meier median times to successful endpoints for each of the two study arms. Time zero is when the ablation procedure begins and the successful outcomes are either complete heart block or junctional rhythm. Patients in whom a successful endpoint is not reached will be censored at the time the procedure is stopped. A log-rank test will also be performed to compare these groups. If there are baseline characteristics that differ between the study arms based on the summaries described above, a Cox proportional hazards model will be fit that includes these baseline characteristics to adjust for these baseline differences in the study arms.

Additional Information

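### The second primary endpoint runs from radiofrequency application, but the primary analysis runs from the start of the ablation procedure, and the plan does not reconcile the two

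*Combined protocol and SAP*

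**What the plan says.** Under Primary endpoints, the second item is "Time from application of radiofrequency energy to acute success". Under Statistical Analyses, "The primary analysis is the estimation of Kaplan-Meier median times to successful endpoints for each of the two study arms", and the next sentence fixes the clock: "Time zero is when the ablation procedure begins". Patients without success are censored when the procedure is stopped. The log-rank test and the conditional Cox model follow in the same paragraph with no other time origin.

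Three other places bear on what the procedure start means. Research Design says "During the ablation each patient will have a 3D electroanatomical map of the his bundle region created in addition to pacing", and the map and pacing are used to choose the target. The secondary endpoints list "Procedure time" separately from "Duration of ablation application". Sample Size Justification gives the use of the result: "This information will then be used to design a fully-powered randomized study to compare these two arms".

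**The concern.** The endpoint and its analysis start their clocks at different events. If the procedure begins before RF energy is delivered, the primary medians include mapping and pacing time that the endpoint definition leaves out, and the declared endpoint has no analysis of its own.

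This matters more than usual here because the per-arm time to success is the pilot's main product. Whoever designs the later trial must know which interval the medians describe. The extra time also cannot be assumed equal between arms. The stated rationale for the MiFi catheter is that its mini electrodes "may enhance the available data for such a signal dependent technique", that is, help with localisation, and localisation is the phase that only one of the two clocks counts. A catheter-related difference in that phase, in either direction, would enter one contrast and not the other.

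**Working it through.** **Step 1: the texts side by side.**

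- Endpoint: starts at RF application and ends at acute success.
- Analysis: starts when the ablation procedure begins and ends at complete heart block or junctional rhythm.

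The end events agree; the starts do not. No sentence equates the two starts, defines the procedure start, or plans an analysis timed from RF.

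**Step 2: which reading is natural?** Four features favour a procedure start that precedes RF:

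- mapping and pacing are placed within the ablation and select the target, so they come before energy is delivered there;
- the inclusion criteria use the term ablation procedure for the whole intervention;
- energy delivery has its own terms (RF application, ablation application);
- procedure time is a separate secondary endpoint.

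**Step 3: what the difference does.** Let R be the time from RF to success and M the time from procedure start to RF. The endpoint is R; the analysis uses P = M + R.

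- If M is the same constant for every patient, median(P) = M + median(R). Ranks do not change, so the log-rank statistic is identical on both clocks.
- If M varies between patients but not by arm, it adds noise to P.
- If M differs by arm, the contrast on P mixes the difference in M with the difference in R.

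**Step 4: illustration.** The documents supply only the arm size of 15. Everything else is assumed: R exponential; M constant or gamma with a coefficient of variation (CV) of 0.3 unless stated; no censoring; rejection when the log-rank |z| exceeds 1.96; 20,000 simulated trials per row. Medians are those of the assumed distributions. All pairs are standard, then MiFi.

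| Median R (min) | Mean M (min) | Median P (min) | Rejection from RF | Rejection from procedure start |
|---|---|---|---|---|
| 8, 4 | 20, 20 constant | 28.0, 24.0 | 0.443 | 0.443 |
| 8, 4 | 20, 20 | 28.9, 24.7 | 0.437 | 0.312 |
| 8, 4 | 20, 25 | 28.9, 29.7 | 0.446 | 0.063 |
| 8, 4 | 25, 20 | 34.1, 24.7 | 0.440 | 0.739 |
| 8, 8 | 20, 20 | 28.9, 28.9 | 0.061 | 0.062 |
| 8, 8 | 20, 25 | 28.9, 34.1 | 0.060 | 0.177 |

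For the last row, a 2-min gap in M gives 0.080 and a 10-min gap 0.459 from procedure start. At a 5-min gap, CV 0.2 gives 0.198 and CV 0.5 gives 0.141. Swapping which arm has the longer M gives 0.179.

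**Step 5: plausibility check.** Exponential medians of 8 and 4 min imply a hazard ratio of 2. With 30 events, the Schoenfeld approximation gives power Φ(√(30/4) × ln 2 − 1.96) = Φ(1.898 − 1.960) = 0.475, close to the simulated 0.44.

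The 0.177 is not a false-positive rate. In that row the arms truly differ in P, so rejection is correct for P. It would mislead only if read as evidence about R, which is what the endpoint definition invites.

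**The case against.** The strongest reply is that the procedure start may be loose wording for the start of energy delivery. The secondary endpoints do use ablation in that narrow sense, so an RF start is not excluded. This stands as a possibility, but the document never says it, and the features in Step 2 point the other way. Even on the lenient reading, time zero needs a clarifying sentence.

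Second, the size is assumed throughout. The large shifts need a 5- to 10-min arm difference in pre-RF time. The plan says only that the catheter may improve signals, not that mapping takes more or less time. That stands: the figures show what could happen, not what will. Equal but variable pre-RF time does, however, lower rejection from 0.437 to 0.312 with no arm difference at all.

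Third, the primary analysis is estimation, with the log-rank test added to it and no alpha or power stated. This is fair, and the case does not rest on rejection rates: even a constant delay moves the medians from 8 and 4 to 28 and 24 min.

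Fourth, an RF clock has a gap of its own, because a patient whose procedure stops before any RF has no time zero. The procedure-start clock avoids this. That is a reason to choose deliberately, not to leave two clocks in place.

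**Conclusion.** The plan is wrong as written on this point and must be corrected before analysis. On the natural reading, the primary medians, log-rank test and Cox model describe a longer interval than the declared endpoint; on the most lenient reading, time zero is undefined.

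The real discrepancy cannot be sized from the documents. The direction of any effect on the arm contrast is also unknown. A constant pre-RF delay would shift both medians equally and leave the log-rank test alone, variable delay would dilute the contrast, and an arm difference could mask, reverse or inflate it. The first primary endpoint, acute success as a yes/no outcome, and the sample size of 30 are unaffected.

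**What to change.** State one time zero in the same words under Primary endpoints and under Statistical Analyses. There are two ways to do it:

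- **Keep the declared endpoint.** Change the analysis text to *time zero is the start of the first RF application of the index procedure*, and add *first* to the endpoint. Report procedure start to success as a labelled secondary analysis. State how a patient who receives no RF is handled.
- **Keep the procedure-start clock.** Change the endpoint definition to match, name the observable event that starts the clock, and report RF to success as secondary.

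The words *first* and *index procedure* are additions, not in the documents. The second must be squared with the Research Design statement that data from any repeat ablation will be included: say whether those data enter the time analysis or are reported separately.

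The cost is a few sentences. The second primary endpoint already requires the RF start time, and the procedure-time endpoint already requires a procedure start time. No patients, procedures or data items are added. Making the change before the data are analysed also prevents the clock from being chosen after the results are seen.

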Microfidelity (MIFI) Ablation Technology versus Standard Ablation Catheter for
Atrioventricular Nodal Ablation

A Comparative Pilot Study of Time to Success

Principal Investigator: [name]

Co-investigators: [name] MD

Introduction

In some elderly patients with atrial fibrillation (AF), especially in combination with heart failure, a rate control strategy may be preferred. When pharmacological therapy is ineffective or not tolerated, it is reasonable to perform atrioventricular (AV) node ablation with ventricular pacing as a class IIA indication per current guidelines [1].

Usually, the procedure is simple and straightforward and complete heart block can be achieved without any difficulty. However, this “simple” procedure can sometimes prove to be a most difficult case. The most common reason for failure to achieve complete heart block is the inability to localize the compact AV node using the His signal with standard intracardiac electrograms. As these patients come to the laboratory in AF, the His signal may be obscured by AF waves. In some patients with a deeper intramyocardial location of the His bundle and compact AV node it becomes necessary to produce deeper ablation lesions using an irrigated catheter to achieve block.

In patients with AF, the target of ablation for the “ablate and pace” approach is the compact AV node, located at the apex of the triangle of Koch. Ideally, ablation is performed at the most proximal penetrating part of the His bundle in order to maintain a proximal automatic junctional rhythm and avoid pacemaker dependence.

Para Hisian pacing is most commonly used to reveal the presence of a septal accessory pathway.

[2-3]

The His bundle is a deep insulated structure and it is difficult to capture it at usual energy outputs. Using a high- output pacing (usually 20 mA at 2 msec) it is possible to directly capture the deeply situated His bundle, which is confirmed by a narrower QRS complex on the paced electrograms. Thus, high-output pacing can be utilized to map the His bundle area in difficult situations.

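### Censoring failed procedures at the stop makes the Kaplan-Meier median unchanged or too short, and no planned analysis reports the acute success proportion (primary endpoint 1)

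*Combined protocol and SAP*

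**What the plan says.** The combined protocol and SAP lists two primary endpoints under Primary and secondary objectives. The first is "Acute success of ablation identified by a junctional rhythm or complete heart block"; the second is the time from radiofrequency application to that success. Study Aims describes the purpose as investigating "the comparative efficacy of high fidelity multi electrode ablation catheters vs the standard bipolar configuration in success of AV nodal ablation".

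Statistical Analyses then gives one primary analysis: "The primary analysis is the estimation of Kaplan-Meier median times to successful endpoints for each of the two study arms". On failures it says "Patients in whom a successful endpoint is not reached will be censored at the time the procedure is stopped". A log-rank test on the same data follows, and a Cox model is added if baseline characteristics differ between arms. The frequencies and percentages mentioned in that section belong to the paragraph on baseline characteristics. No proportion, interval or test is described for acute success.

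Sample Size Justification sets 15 patients per arm, calls the study a pilot whose main purpose is to estimate time to success, and says of the results: "This information will then be used to design a fully-powered randomized study to compare these two arms".

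Two passages bear on how many failures to expect and when they would stop. The Introduction says "Usually, the procedure is simple and straightforward and complete heart block can be achieved without any difficulty", but it also discusses failures: "The most common reason for failure to achieve complete heart block is the inability to localize the compact AV node". Research Design says "Data will be collected until the primary endpoint of success is achieved", which suggests that attempts are not abandoned early.

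**The concern.** Censoring is neutral when the patient could still have the event later and we merely stopped looking. Here the stop is itself the outcome: the index procedure is over and did not succeed. The Kaplan-Meier estimator removes that patient from the risk set and in effect spreads the patient's weight over those still being treated, as if the patient would have gone on to succeed as they did. If the target is the time by which half of all randomized patients have been successfully ablated, the planned median can be too short. The final height of the curve can also overstate the proportion who succeed.

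A success proportion reported beside the curve would show the failures. None is planned, although it is the first primary endpoint. The stake is the next trial: its designers need both how fast success comes and how often it comes at all, and a curve that reaches 100% despite failures could mislead them on the second.

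**Working it through.** **Inputs.** 15 patients per arm (Sample Size Justification); failures censored at the stop and Kaplan-Meier median per arm (Statistical Analyses). Failure rate, stop times and the distribution of success times are not in the documents. The plan gives no power, effect size or precision target, so it has no figure of its own to reproduce.

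**Direction.** Kaplan-Meier: S(t) = product over success times of (1 − d/r), with d successes among r at risk. Keeping failures in the risk set makes r larger or leaves it equal at every success time, so each factor is larger or equal. The planned curve therefore shows success as early or earlier at every time, and its median cannot be later. With untied times, S reaches 0 (100% success) exactly when the last observation is a success.

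**Size of the median shift, whatever the distribution.** Take the median as the first time S ≤ 0.5. With failures kept at risk, S after j successes is (15 − j)/15, so the median is the 8th success (7/15 = 0.467). As planned, the largest shift occurs when all k stops precede the first success; then S = (15 − k − j)/(15 − k):

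- k = 1: 7/14 = 0.500 at j = 7, so the 7th success. If the stop comes just after the first success, S = (14/15) × (14 − j)/13, which is 0.503 at j = 7 and 0.431 at j = 8, so the 8th.
- k = 2: 6/13 = 0.462 at j = 7, so the 7th.
- k = 3: 6/12 = 0.500 at j = 6, so the 6th.

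Enumerating every ordering confirms that the planned median is the 7th or 8th success for k = 1 or 2, and the 6th, 7th or 8th for k = 3. For k = 1 the 7th arises only if the stop precedes the first success. If all stops follow the 8th success, it is always the 8th.

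**Worked arms (invented times).**

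| Successes (min) | Stops (min) | Median, planned / kept at risk | Final success, planned / kept at risk |
|---|---|---|---|
| 14, at 2 to 15 | 3.5 | 9 / 9 | 100% / 93% |
| 12, at 2 to 13 | 2.5, 3.5, 4.5 | 8 / 9 | 100% / 80% |
| 12, at 2 to 13 | 14, 15, 16 | 9 / 9 | 80% / 80% |

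Second row: after 4 min S = (14/15)(12/13)(10/11) = 0.783 with 9 at risk. At 7 min S = 0.783 × 6/9 = 0.522, and at 8 min 0.783 × 5/9 = 0.435.

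**Percentages under assumptions.** With constant hazards summing to 1 and failure fraction f, the Kaplan-Meier median is ln 2/(1 − f). The median of the cumulative incidence of success is −ln(1 − 0.5/(1 − f)).

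| f | Planned | Kept at risk | Shortening |
|---|---|---|---|
| 1/15 | 0.743 | 0.767 | 3.2% |
| 0.10 | 0.770 | 0.811 | 5.0% |
| 0.20 | 0.866 | 0.981 | 11.7% |
| 0.40 | 1.155 | 1.792 | 35.5% |

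This model lets failures stop on the same time scale as successes. To vary that, 6,000 arms of 15 were simulated per scenario. Success times were exponential, Weibull (shape 2) or lognormal (sigma 0.5), and stops were uniform over multiples of the median success time. The results below are for arms with at least one failure; ranges are over the three distributions.

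| f | Stops (× median) | Medians identical | Curve ends at 100% |
|---|---|---|---|
| 1/15 | 0.25–1 | 49–72% | 100% |
| 1/15 | 0.5–2 | 91–93% | 90–99% |
| 1/15 | 2–4 | 99.9–100% | 7.5–78% |
| 0.20 | 0.25–1 | 14–29% | 100% |
| 0.20 | 2–4 | 98–100% | 3–67% |

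With f = 1/15 and stops at 6–8 times the median, the curve ended at 100% in 0–10% of arms. The planned median was never the longer of the two.

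**Chance that the issue arises.** P(at least one failure in 30) = 1 − (1 − p)^30: 45%, 79% and 96% for assumed failure rates p of 2%, 5% and 10%.

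**The case against.** The strongest reply is that censoring at the stop is a recognised cause-specific analysis: it describes the rate of success while ablation continues. On that basis the log-rank test and Cox model are valid, and this stands. The plan does not say, however, that its median has that conditional meaning, and a median time to success per arm will naturally be read as applying to all patients in the arm.

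A second reply is that the effect on the median is near zero in the setting that the Introduction and Research Design suggest, with few failures and late stops. This also stands. The larger percentages above need failure rates of 20% or 40%, which no passage supports, and a reader should not infer that the median is known to be materially biased.

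A reader might also infer that the stated aim has no planned analysis at all. The documents do not support that. The log-rank and Cox analyses use success as their event and so bear on comparative efficacy, and Sample Size Justification names time to success as the primary aim. The gap is narrower: the success proportion itself is not reported. The count could be recovered from the data, but that does not make it a prespecified analysis of a primary endpoint.

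**Conclusion.** The point holds and should be fixed. For the all-patient target, the planned median is right or too short, by at most one ordered success with one or two failures in an arm and at most two with three. With few, late failures it will usually not move. The final height of the curve is more fragile: with a single failure in an arm, it reads 100% instead of 93% (14/15) unless that stop is the longest observed time. The direction and the ordered-success limits need no assumption about time distributions; every percentage shortening does, because the documents give neither failure rates nor stop times. The absence of an acute success proportion is read directly from the text and depends on no assumption.

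**What to change.** Replace the censoring sentence under Statistical Analyses with wording such as:

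> Patients whose index procedure ends without success are counted as failures and remain in the risk set beyond the longest observed time to success in either arm, which is equivalent to estimating the cumulative incidence of success. The median is reported as not reached if fewer than half of an arm succeed. The acute success proportion (primary endpoint 1) is reported per arm with an exact 95% confidence interval, and the between-arm difference with a 95% confidence interval. The log-rank and Cox analyses with censoring at the stop are retained and labelled cause-specific. The time of, and reason for, each stop without success are recorded.

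The method for the interval on the difference should be named. If only one change is made, it should be the success proportion and its difference.

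The cost is a few sentences, a one-line recode and one data field for the reason for stopping. If no procedure fails, the time results do not change. The downsides are that the median may be longer or not reached in an arm with many failures, and that the intervals are wide at 15 per arm: 15/15 = 100% (78 to 100%), 14/15 = 93% (68 to 99.8%), 12/15 = 80% (52 to 96%). A log-rank test on the recoded times would mix speed with failure, which is why the cause-specific version is kept.

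### The secondary Cox model takes every baseline characteristic that appears to differ between arms, with no maximum, against at most 30 events; if about five or more enter, its 95% interval under-covers and its hazard ratio is less precise than the unadjusted one.

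*Combined protocol and SAP*

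**What the plan says.** The Sample Size Justification fixes the size of the study, "Thirty patients will be randomized (15 in each study arm", and its purpose, which is estimation by arm: "This is a pilot study in which the primary aim is to estimate the time until successful end point in each of the two study". No power, significance level or effect size is given.

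Under Statistical Analyses, "The primary analysis is the estimation of Kaplan-Meier median times to successful endpoints for each of the two study arms". A log-rank test accompanies it. On events, "the successful outcomes are either complete heart block or junctional rhythm", and "Patients in whom a successful endpoint is not reached will be censored at the time the procedure is stopped".

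Baseline characteristics are compared through descriptive summaries and plots, and "if there are individual baseline characteristics that differ between the study arms, these characteristics will be included a regression analysis". The purpose given there is to lower the variance of the between-arm comparison. For the time-to-success endpoint the same trigger applies: "a Cox proportional hazards model will be fit that includes these baseline characteristics". The purpose given there is to adjust for the baseline differences.

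The Cox model is therefore conditional and secondary. The plan does not say which characteristics are candidates, how large a difference must be to count, or how many may enter. It names no penalised or small-sample method.

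**The concern.** Each patient contributes at most one first success and failures are censored, so the Cox model has 30 events at best. With 15 patients per arm, sizeable chance differences in baseline characteristics are common even under perfect randomisation. A rule that enters all of them can produce a model with few events per coefficient. In such a model the usual standard error understates the true variability of the treatment coefficient, and a real effect tends to be estimated as too large.

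What is at stake is how far the adjusted hazard ratio and its interval can be trusted. It is the only hazard ratio in the plan, since the log-rank test gives a p-value and the Kaplan-Meier analysis gives medians. The primary result does not depend on it.

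**Working it through.** **Inputs from the document.** 30 patients, 15 per arm; at most 30 events; every characteristic that differs enters; no list, threshold or maximum. The sample size has no stated derivation, so beyond 2 × 15 = 30 there is no figure to reproduce.

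**Assumptions.** Candidate characteristics: 5 to 15, independent. Threshold for a difference: a standardised difference above 0.3 or 0.5. Censoring: 10%, so about 27 events. Exponential times, Wald 95% intervals.

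**Step 1: how many covariates enter by chance.** The standard error of a standardised difference is √(2/15) = 0.365.

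- Threshold 0.3: 0.3/0.365 = 0.82, so each characteristic enters with probability 2 × [1 − Φ(0.82)] = 0.41.
- Threshold 0.5: 0.5/0.365 = 1.37, so each enters with probability 0.17.

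Binomial counts follow:

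| Candidates | Threshold | Mean entering | P(5 or more) |
|---|---|---|---|
| 5 | 0.3 | 5 × 0.41 = 2.1 | 0.01 |
| 10 | 0.5 | 10 × 0.17 = 1.7 | 0.02 |
| 15 | 0.5 | 15 × 0.17 = 2.6 | 0.10 |
| 10 | 0.3 | 10 × 0.41 = 4.1 | 0.40 |
| 15 | 0.3 | 15 × 0.41 = 6.2 | 0.81 |

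Simulated trials gave similar figures; for the last row they ranged from about 0.76 to 0.84. A threshold near p < 0.05 lets in under one covariate on average from 15.

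**Step 2: what a given number of covariates does.** Cox fits to 1,500 simulated trials per setting, with covariates that do not predict outcome and a fixed number in the model:

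| Covariates | HR 1: coverage | HR 1: SD of log HR | HR 1: median model SE | HR 2: median estimate | HR 2: coverage |
|---|---|---|---|---|---|
| 0 | 93.9% | 0.44 | 0.40 | 2.13 | 94.8% |
| 2 | 93.2% | 0.50 | 0.43 | 2.15 | 94.0% |
| 5 | 91.1% | 0.60 | 0.48 | 2.26 | 91.3% |
| 8 | 88.8% | 0.73 | 0.55 | 2.58 | 89.1% |
| 10 | 87.9% | 0.84 | 0.59 | 2.71 | 85.5% |

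Monte Carlo error of coverage is about 0.6 to 0.9 percentage points. With five covariates the interval half-width on the log scale is 1.96 × 0.48 = 0.94. That is wider than the unadjusted 1.96 × 0.40 = 0.78, but short of the 1.96 × 0.60 = 1.18 that the true variability calls for.

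**Step 3: the plan's own selection rule.** When covariates are selected by observed imbalance and about six enter, coverage is about 89% to 93%, and the SD of the log hazard ratio is 0.70 to 0.80 against a model SE of 0.57 to 0.59. One set of runs with partly binary candidates went down to 86.9%. Over the assumed settings the SD was 0.50 to 0.80 adjusted, against 0.41 to 0.47 unadjusted.

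**Step 4: direction of the estimate.** At a true hazard ratio of 1 the median estimate stays close to 1 throughout. At a true hazard ratio of 2, non-prognostic covariates inflate the estimate as in the table. With prognostic covariates selected by imbalance, medians across the runs were 1.67 to 2.23. Prognostic covariates left out pull the estimate towards 1 and offset the inflation.

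**The case against.** The strongest reply is that the plan does not say enough to convict it. With a short list or a strict reading of a difference, one or two covariates enter and little is lost. Ten candidates at 0.5 give five or more covariates in only 2% to 3% of trials. This stands: a reader might infer that the model will usually be overfitted, but the documents give neither the candidate count nor the threshold that this would need.

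A reader might also infer that the hazard ratio is pushed away from 1. Step 4 does not support that as a general statement. It needs a true effect and many covariates, and it can be offset or reversed.

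A third tempting inference is that the full trial will be sized on an inflated hazard ratio and be too small. The Sample Size Justification says "This information will then be used to design a fully-powered randomized study to compare these two arms". In context this most naturally refers to the estimated time to success in each arm, and no section says that the Cox hazard ratio will be used. Any hazard ratio from 30 patients is also a weak basis for sizing: the unadjusted SD of its log is already above 0.4.

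Finally, the adjusted interval is wider than the unadjusted one, so readers would see some of the added uncertainty. That is true, but it does not show all of it.

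What survives is that the plan states a rule with no upper limit. The rule can produce an unreliable model, and under the assumed settings it raises the variance that adjustment was meant to reduce.

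**Conclusion.** The point holds in a conditional form. The rule sets no limit on the covariates in a secondary Cox model with at most 30 events. Under the assumed 10 to 15 candidates and thresholds of 0.3 to 0.5, about 2 to 6 enter on average. With about five or more, 95% intervals cover roughly 89% to 93%, the log hazard ratio is more variable than without adjustment, and a non-null hazard ratio can be exaggerated. With one or two covariates the loss is small.

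The size rests on the assumed candidate count, threshold, censoring and exponential times, none of which the plan states. The Kaplan-Meier medians and the log-rank test are not affected. The change is worth making because it is cheap and clearly better than the stated rule, not because the pilot's primary result is at risk.

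**What to change.** Under Statistical Analyses:

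- Replace the rule based on observed differences with a Cox model containing treatment and at most one or two prognostic baseline covariates, named before outcome data are seen.
- Report all other baseline imbalances descriptively only.
- Add an unadjusted Cox hazard ratio with its 95% interval beside the Kaplan-Meier medians and the log-rank test. The plan does not currently contain one.
- Call the adjusted model a sensitivity analysis.

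Both the limit and the advance naming are needed. Six fixed, truly prognostic covariates still gave 88.8% to 89.7% coverage and a median of 2.42 at a true hazard ratio of 2. With two fixed covariates the model has three coefficients, or 27/3 = 9 to 30/3 = 10 events each. Coverage was then 93.2% to 94.0% in the main runs and 91.6% to 94.2% in a second set. Two covariates do not reduce the SD below the unadjusted value (0.50 against 0.44 when they do not predict outcome), so the text should not promise a variance reduction. A penalised (Firth) fit would be a reasonable alternative safeguard.

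The cost is a few sentences of analysis text, with no extra patients or data. The small downside is that chance imbalances in other characteristics are described but not adjusted for.
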